5. Spouse, significant other, or other family member involved in decision making for child <18 years if parent/legal guardian of child already enrolled into this study.

Total number of subjects to be studied (including those screened for eligibility) in Qualitative Needs Assessment Interviews and Beta Testing:

Up to 50. Sample size is dependent on data saturation during analysis and need for verification of findings.

Total number of subjects to be studied in Hindi Beta Testing

Up to 50 individuals will be consented for participation in the Hindi Beta Testing study. Sample size is dependent on data saturation during analysis and need for verification of findings.

Total number of subjects to be studied (including those screened for eligibility) in Testing of Decision Aid:

Cohort A: 120

Cohort B: 25

Cohort C: Up to 50 (depending on number of health care providers providing care to patient population in this study).

Sample Size Calculations for the Randomized Clinical Trial (Cohort A)

We assume that patient involvement is 30% with standard care and we can double this with the intervention. Based on 90% power and 0.05 significance level we will require 110 patients, 55 in each group for comparing 2 binomial proportions⁴⁴. To account for attrition we propose to recruit 120 patients, 60 in each group treatment group with 20 in each of 3 age groups.

Total Duration of Participation

Qualitative Needs Assessment Interviews: 6 weeks

Decision Aid Testing: Up to 12 months

Recruitment Methods

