Qualitative analysis will be performed using qualitative descriptive methods which is influenced and a similar to interpretive descriptive analysis. Qualitative descriptive^{45,46} analysis requires less interpretation than other types of qualitative analysis, such as phenomenological or interpretive description. Qualitative description lends itself to a more straightforward analysis that, by the nature of its methods, lends itself to this study. Analysis of these data will rely on components of the Ottawa Decision Support Framework for development of a codebook. This framework provides operational definitions of needs in the decision making process, such as decisional conflict (uncertainty), knowledge and expectations, personal values, and support/resources available. Additionally, data will be quantized or translated to numerical data for improved understanding of results⁴⁷. This method of analysis allows for quantification of themes, patterns, and idiosyncrasies unique to qualitative research that may otherwise be discarded as outliers in quantitative analysis⁴⁷.

We propose a randomized controlled trial of decision aid vs. usual care to determine its impact on previously defined endpoints measuring decisional process and decisional quality.

Avoidance of bias

Selection biases occur when the groups to be compared are different. We anticipate that randomization will avoid selection bias as well as volunteer or referral bias. A *drop out analysis will be carried out to determine the contribution of attrition bias*. Measurement biases involve systematic error that can occur in collecting relevant data and include, insensitive measure bias, expectation bias, recall or memory bias, attention bias, and verification or work-up bias. Systematic validation of the decision aid will avoid *insensitive measure bias* which occurs when instruments used are not sensitive enough to detect what might be important differences in the variable of interest. The risk of *Expectation bias*, when observers may err in measuring data toward the expected outcome will be avoided by masking or blinding the reviewer of the survey about the arm to which the patient was randomized. Recall or memory bias which can occur if outcomes being measured require that subjects recall past events will be avoided by administering surveys within days of the interaction with their health care provider.

Human Subjects

Protected Health Information

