Research staff directly involved in the study will have access to data collected during this study. Paper documents will be filed in a locked filing cabinet in a secure office setting. Electronic data will be maintained on a secure Hematology/Oncology share-drive with limited access behind a secure firewall at Emory University. Participant data will be identified with a unique number. The key connecting the participant to the ID number will be maintained separately from the study data and will be destroyed upon completion of the study, to include dissemination of findings. The ID key will be accessible only to members of the research team. All audio recordings will be identified on the recording with the unique participant identification number. All transcripts will be identified using the participant identification number and names of parents and health care providers will be indicated with "XXX" in the transcription. Audio transcriptions will be destroyed after transcription is complete and verified, analyzed and findings are disseminated.

The data and safety monitoring team will include the Principal Investigator and the study coordinator. Meetings will occur every 3 months from time of enrollment of the first patient. DSMP reports will be generated for each meeting. Any information regarding increased risks, modifications necessary to ensure patient safety, and adverse events will be discussed and submitted to the IRB according to established guidelines. All study data reviewed and discussed during these meetings will be kept confidential. Any breach in confidentiality will be reported to the IRB and regulatory agencies. The investigator will continue to review all available information and study results regarding this patient population. The PI will report to the IRB within 24 hours any serious adverse event occurring that is associated with this research study. Unexpected adverse events of moderate severity in association with the research intervention will be reported to the IRB within 5 business days. Reporting of adverse events to sponsors and federal agencies will be the responsibility of the investigator.

Withdrawal from Study

The participant may withdraw from the study at any time by notifying the PI and/or the research team. All data collected up until the point of withdrawal will be included in data analysis. No further data will be collected.

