The participant may be withdrawn from the study if the participant does not participate in the educational process of usual care or if the participant assigned to intervention does not view the website prior to the next scheduled clinic appointment or does not show for the next appointment and does not reschedule that appointment within 4 weeks of the originally scheduled appointment.

Compensation

Study participants, (patients, parents/legal guardians) will be provided with a \$25 gift card for each completed set of survey questions.

Participants (patients, parents/legal guardians and caregivers) will be provided with a \$25 gift card for completion of each qualitative interview.

Healthcare providers and stakeholders will be given a sickle cell tie, bowtie or scarf for their participation in this study.

There will be no compensation provided for participation in the Hindi beta testing.

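### The plan relies on an undefined drop-out analysis to settle attrition bias, with no analysis set, missing-data method or sensitivity analysis to show how missing outcomes could move the arm comparison

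*Combined protocol and SAP*

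**What the plan says.** Avoidance of bias (under Analytic Methods) gives attrition one sentence: a "drop out analysis will be carried out to determine the contribution of attrition bias". No content, model or decision rule follows.

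Three other places bear on loss:

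- Sample Size Calculations for the Randomized Clinical Trial (Cohort A) assumes: "We assume that patient involvement is 30% with standard care and we can double this with the intervention". It then states: "Based on 90% power and 0.05 significance level we will require 110 patients, 55 in each group for comparing 2 binomial proportions". The allowance for loss is: "To account for attrition we propose to recruit 120 patients, 60 in each group treatment group".
- Withdrawal from Study says: "All data collected up until the point of withdrawal will be included in data analysis. No further data will be collected".
- The same section lets the team withdraw a participant for, among other reasons, this one: "if the participant assigned to intervention does not view the website prior to the next scheduled clinic appointment".

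The documents name no analysis population, no method for a missing Visit 2 or Visit 3 outcome, and no sensitivity analysis.

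**The concern.** The sentence gives the drop-out analysis a job that, as usually understood, it cannot do. Comparing leavers with stayers on recorded data shows whether they differed on what was measured before they left. The bias in the arm comparison depends on the outcomes that were not measured. A finding of no difference could therefore be reported as reassurance while the estimate is still off, and readers would have no measure of how far off it could be.

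The other provisions do not fill the gap. Raising 110 to 120 protects power. Using data up to withdrawal keeps earlier surveys, but does not say how a participant without the later outcome enters the comparison.

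The plan also contains a route by which loss can depend on arm and engagement. Not viewing the website is a ground for withdrawal that can arise only in the intervention arm. It selects on engagement, which lies close to the outcome used for sizing, patient involvement. Once withdrawn, the participant supplies no more data.

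**Working it through.** **Inputs.** From the sample size section: 30% involved under usual care, 60% with the decision aid, significance level 0.05, power 90%, 55 per arm needed, 60 per arm recruited. Implied loss: 60 − 55 = 5 per arm, or 5/60 = 8.3%. Assumptions made here: two-sided test (the section does not say), equal loss in both arms, and the planned rates holding among completers.

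**Step 1: the plan's own figure.** Pooled-variance formula without continuity correction:

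n = [1.960·√(2·0.45·0.55) + 1.282·√(0.30·0.70 + 0.60·0.40)]² / 0.30² = (1.379 + 0.860)² / 0.09 = 55.7

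This rounds up to 56 per arm, 112 in all, against the stated 110. Power at 55 per arm is 89.6%. The figure reproduces to within 2 patients.

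**Step 2: the planned result among completers.** 33/55 v 16.5/55, difference 30 points, z = 0.30/√(0.45·0.55·2/55) = 3.16, p = 0.0016.

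**Step 3: all 60 per arm.** Let k be the number lost per arm, and let qI and qC be the unseen proportions involved among the missing in the intervention and control arms. Then

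d = 0.30·(60 − k)/60 + k·(qI − qC)/60, and z = d / √(p̄(1 − p̄)·2/60), where p̄ is the pooled proportion.

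With k = 5:

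| Assumption about the missing | Control | Intervention | Difference (points) | z | p |
|---|---|---|---|---|---|
| Extreme worst: qI = 0, qC = 1 | 21.5/60 = 35.8% | 33/60 = 55.0% | 19.2 | 2.11 | 0.035 |
| qI = 0.2, qC = 0.8 | 20.5/60 = 34.2% | 34/60 = 56.7% | 22.5 | 2.47 | 0.013 |
| Rates reversed: qI = 0.3, qC = 0.6 | 19.5/60 = 32.5% | 34.5/60 = 57.5% | 25.0 | 2.75 | 0.006 |
| All missing not involved | 16.5/60 = 27.5% | 33/60 = 55.0% | 27.5 | 3.06 | 0.002 |
| Extreme best: qI = 1, qC = 0 | 16.5/60 = 27.5% | 38/60 = 63.3% | 35.8 | 3.94 | <0.001 |

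With k = 6, the extreme worst case is 22.2/60 = 37.0% v 32.4/60 = 54.0%: 17.0 points, z = 1.87, p = 0.062. The three middle rows become 21, 24 and 27 points, with p = 0.021, 0.008 and 0.003.

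**Step 4: how firm is the point at which significance is lost?** Step 3 uses fractional counts. With whole numbers, in the extreme worst case:

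| Lost per arm | Completers (control, intervention) | Worst case over 60 | Difference (points) | Uncorrected chi-square p | Fisher p |
|---|---|---|---|---|---|
| 5 | 16/55, 33/55 | 21 v 33 | 20.0 | 0.028 | 0.043 |
| 5 | 17/55, 33/55 | 22 v 33 | 18.3 | 0.044 | 0.067 |
| 6 | 16/54, 33/54 | 22 v 33 | 18.3 | 0.044 | 0.067 |
| 6 | 16/54, 32/54 | 22 v 32 | 16.7 | 0.067 | 0.098 |

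The crossing lies at about 5 to 6 per arm and moves with the test and with rounding by one person.

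**Step 5: what the drop-out analysis adds.** qI and qC are exactly what leavers do not supply. The same completer data are compatible with every row of the Step 3 table, from 19.2 to 35.8 points. A comparison of recorded features may make some rows more plausible than others, but it cannot select one.

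**The case against.** The strongest reply is that the plan never says what its drop-out analysis is, so it is unfair to assign it a narrow meaning and then fault it; the term could cover sensitivity analyses. It is right that the analysis is undefined. But nothing in the text provides such analyses, and in its usual sense the method does not meet the stated purpose.

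A reader might infer that the plan commits to a completers-only comparison. It does not. Moving from 110 to 120 is ordinary inflation for power and sets no analysis population, and "All data collected up until the point of withdrawal will be included in data analysis" points towards using partial data. The supportable statement is that the analysis set is not given.

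A reader might also infer that the planned attrition would overturn the result, or that significance vanishes at exactly 6 lost per arm. Neither holds. The worst case requires every missing intervention participant to be uninvolved and every missing control to be involved. Even then, the planned result survives a loss of 5 per arm under the uncorrected test on fractional counts. Step 4 shows that no exact threshold can be claimed.

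The plan has features that should limit loss: a gift card for each completed survey set, paper or electronic completion, surveys put at 20 to 30 minutes, and monthly contact (worded around website access). They make heavy loss less likely but do not replace a missing-data method. That non-response will in fact depend on involvement is not shown in the documents. The website rule only makes it possible.

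**Conclusion.** The point stands as a gap in method. The only stated safeguard against attrition bias is undefined and, as usually understood, cannot show how missing outcomes would move the arm comparison; nothing else in the documents does so.

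At the plan's implied loss of 5 per arm, the difference over all randomised participants is bounded between about 19 and 36 points around the planned 30. The lower figure (p about 0.035) is an extreme bound, not an expected bias. Less extreme adverse assumptions leave 22.5 to 27.5 points and remain significant. These figures rest on 60% v 30% among completers, equal loss by arm and a two-sided uncorrected test. Greater loss, unequal loss or a smaller observed effect would change them, and the documents give no figures for those cases.

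This should be settled before outcomes are seen, but it does not threaten the feasibility of the trial.

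**What to change.** Replace the drop-out sentence with a short missing-data section that does the following:

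1. States that the main comparison is by randomised arm and includes all randomised Cohort A participants.
2. States how missing Visit 2 and Visit 3 outcomes are handled, for example by multiple imputation using arm, age group and the Visit 1 scores actually collected (such as knowledge, decisional conflict and decision self-efficacy). An earlier involvement score cannot be assumed: the involvement scale named under Expected Outcomes is in none of the Cohort A survey lists, including those under Cross-Over.
3. Adds a tipping-point table that varies the assumed outcome of the missing separately in each arm and shows where the conclusion changes, with the worst case included and labelled as a bound.
4. Keeps the comparison of leavers with stayers as description only.
5. Reconciles Withdrawal from Study with this analysis set. As written, an intervention participant can be withdrawn for not viewing the website and then contributes no later outcome.

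The cost is SAP wording, a little programming and possibly slightly wider intervals. Items 1 to 4 need no extra participants or visits.

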We will collect demographic information from parent/legal guardian of children (<18 years of age) including but not limited to age, gender, race, education, marital status, employment and religion. Additionally we will collect demographic information about the child including but not limited to age, gender, race, education, number of full and half siblings). Additionally patients and parents/legal guardians of patients will be asked to self-report information regarding themselves or the patient they care for including but not limited to patient age, gender, education level, marital status, genotype, insurance type, history of HLA typing, number of hospitalizations for sickle cell related complications in the past 2 years. No PHI will be accessed.

Participants will be asked to complete the following study surveys at within 2 weeks following their office/clinic visit, questionnaires will be available in paper version and electronically:

- Acceptability of education (*8 multiple choice, 2 short answer*)
- Decision Self-Efficacy Scale (*11 multiple choice*)
- Decisional Conflict Scale (*16 multiple choice*)
- Values survey (*14 multiple choice, 6 fill in the blank*)
- Realistic Expectations (*multiple choice*)
- Preparation for Decision Making Scale (*10 multiple choice*)
- Knowledge Survey (*25 multiple choice*)
- Choice Predisposition and Decision (*1 multiple choice and 4 fill in the blank*)
- Stage of Decision Making (*10 multiple choice*)

Participants => 18 years of age will complete:

- Emotional distress Anxiety – short form 6a – participant version
- Depression – short form 6a – participant version
- Fatigue – short form 6a – participant version
- Pain interference – short form 6a – participant version
- Physical Function – short form 8b – participant version

- Ability to participate in social roles and activities – short form 6a – participant version

Participants of children <18 years of age will complete:

- Fatigue – short form 10 – parent proxy
- Mobility – short form 8 – parent proxy
- Peer relations – short form 7 – parent proxy
- Anxiety – short form 8b – parent proxy
- Depressive symptoms – short form 6b – parent proxy

It is anticipated that these surveys will take 20-30 minutes to complete within 2 weeks following each visit. Surveys may be available via paper version and electronically.

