Participants in Cohort A who are assigned to the control group will receive education regarding treatment consideration from their healthcare provider/team as per standard practice (usual care).

Participants in Cohort A who are assigned to the intervention group will receive education regarding treatment consideration from their healthcare provider/team as per standard practice. Additionally, they will be provided access to the decisional aid and will be provided with a unique access ID and password for purposes of this study. Participants will receive follow-up monthly via telephone call and/or e-mail to verify ability to access and navigate through website.

Visit 2

Participants will be scheduled for the second research visit to coincide with the completion of education presented by the healthcare provider/team. Participants will be asked to complete the study surveys within 2 weeks following the office/clinic visit via paper version or on-line. Self-report information regarding themselves or the patient they care for will be updated relating to sickle cell disease management and complications since Consent/Visit 1. Participants will receive follow-up monthly via telephone call and/or e-mail to verify ability to access and navigate through website.

Visit 3

Participants will be scheduled for the final research visit within 4 months of the completion of education and discussion with their healthcare provider/team. Participants will be asked to complete the study surveys as well as either via paper versions or online within 2 weeks following this office/clinic visit:

- Decision Regret Scale (*5 multiple choice*)
- Additionally, a qualitative interview will be conducted with the participants within 4 weeks of visit 3 to evaluate the extent to which the method of educational tools (standard practice or decision aid) helped the participant to recognize that a decision needs to be made regarding treatment of sickle cell disease, to understand the values that affect the decision, and understand if and how these values were addressed with the health care provider. Interviews will take approximately 30-45 minutes for completion. Interviews will

be audio recorded and transcribed verbatim for later analysis. Interviews will be conducted in a private setting, away from family members and clinical staff.

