After consenting to participate in the study in-person or via telephone demographic information will be collected from health care providers including but not limited to education, years of practice, age, and gender after Cohort A visit 3. Health care providers will be asked to complete one questionnaire after Cohort A visit 3 interview and again after Cohort A visit 4 interview. It is anticipated that this survey will take no more than 5 minutes to complete.

- Physician determination of patient readiness for treatment decision making in sickle cell disease

Study Population

Study population may be drawn from among sickle cell patients, any patient who is post-bone marrow transplant for sickle cell disease, and the caregivers of pediatric patients who receive care at the Aflac Cancer and Blood Disorders Center of Children's Healthcare of Atlanta (Egleston, Hughes Spalding, and Scottish Rite locations) and various sickle cell clinics across the United States. Contact will be made with physicians and sickle cell foundations through listserves, professional conferences, and seminars regarding this study. Recruitment flyers will be provided for placement in patient/parent/caregiver common areas to physicians, clinics, and sickle cell foundations known to the research team across the country after permission has been obtained from these entities. Recruitment flyers will request individuals to contact the research team if interested in participation. Discussion with physicians will occur prior to placement of flyers for Decision Aid website testing to obtain physician understanding of the study.

Recruitment of Women and Minorities as Research Subjects. Equal number of women and men are likely to be recruited. Majority of the patients will be of minority ethnic origin because of the demographics of distribution of SCD. The racial, gender and ethnic characteristics of the proposed subject population reflects the demographics of the study sites. We shall attempt to recruit subjects in respective proportion to these demographics. No exclusion shall be based on race, ethnicity, or gender.

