There is a minimal risk of breach of confidentiality of health information even though no medical data will be collected from official medical records/charts and only self-reported information will be collected from participants. Participants have the right to refuse to answer self-reported questions regarding their health or the health of family members. Any private data reported by participants related to sickle cell disease will be maintained in a confidential file within the secure offices of the Hematology/Oncology Department. When collecting data from third parties (i.e. parents, caregivers, family) no names of patients with sickle cell disease, names of health care providers/medical facilities will be obtained. This is meant to decrease any possibility of patient identification. Participants in Cohort A and Cohort B will be informed that health care

providers will be made aware of their participation in Testing of Decision Aid due to the participation of health care providers in this study, Cohort C.

Age range

8 to 80 years, inclusive

Inclusion Criteria

Qualitative Needs Assessment Interviews and Beta Testing

1. Individuals with sickle cell disease ages 8 to 80 years, inclusive
2. Individuals who are post- bone marrow transplant for sickle cell disease
3. Parents/legal guardians/caregivers (including significant others, family and friends) of individuals with sickle cell disease (newborn to 80 years) directly involved in decision making with/for that individual
4. Parents/legal guardians/caregivers (including significant others) of individuals who are post-bone marrow transplant for sickle cell disease who are directly involved in decision making with/for that individual
5. Stakeholders involved in any aspect of sickle cell disease
6. Healthcare providers who are directly involved in sickle cell healthcare, including but not limited to physicians, nurse practitioners, physician assistants, social workers, and nurses.
7. All participants will be able to comprehend English
8. Patients <18 years may also participate in Testing of Decision Aid only if they complete the Needs Assessment Interview first.

Beta Testing (additional)

1. Access to the internet via smartphone, personal computer, tablet or other device allowing for access to the decision aid website for telephone interviews. (Computers may be provided for access during in-person interviews by the research team.)
2. Patients will have sickle cell disease.

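### The claim that expectation bias is avoided rests on masking the survey reviewer, which can protect only the few free-text survey items; participants know their arm, and no masking is described for provider ratings or interview coding

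*Combined protocol and SAP*

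**What the plan says.** Analytic Methods, Avoidance of bias, describes expectation bias as arising "when observers may err in measuring data toward the expected outcome" and says it "will be avoided by masking or blinding the reviewer of the survey about the arm to which the patient was randomized". No other sentence in the document describes masking.

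Other sections show who produces the data:

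- **Cohort A surveys** (Consenting/Visit 1): "Participants will be asked to complete the following study surveys at within 2 weeks following their office/clinic visit", on paper or electronically. Most items are multiple choice. A few instruments add free text, such as the Values survey ("14 multiple choice, 6 fill in the blank").
- **Allocation** (Cohort A): both groups get usual education. The intervention group also gets personal log-in details for the website.
- **Cohort C**: providers complete one form, "Physician determination of patient readiness for treatment decision making in sickle cell disease". Study Population adds that "providers will be made aware of their participation in Testing of Decision Aid".
- **Visit 3 interview**: its purpose is "to evaluate the extent to which the method of educational tools (standard practice or decision aid) helped the participant" in reaching a decision.
- **Interview analysis** (Analytic Methods): a codebook is applied, and "data will be quantized or translated to numerical data for improved understanding of results".
- **Transcripts** (Data and Safety Monitoring Plan): they carry the participant number, and the names of parents and providers are replaced by a placeholder. Removal of arm information is not mentioned.

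**The concern.** The plan's own definition concerns people who measure with an expectation in mind. The safeguard should therefore sit with those people, but it sits mainly with someone handling forms that leave almost nothing to interpret. For a self-completed scale the participant is in effect the observer, and the participant knows the arm. Where a third party does judge, the plan is silent on masking.

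What is at stake is how the results can be read. A difference in favour of the aid on a self-reported scale, a readiness rating or a theme count could partly reflect expectation. As it stands, the sentence invites the reader to exclude that explanation.

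**Working it through.** **1. What reviewer masking can reach.** The inputs are the item counts in the Cohort A Visit 1 survey list, for instruments whose counts are given.

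| Instrument | Multiple choice | Free text |
|---|---|---|
| Acceptability of education | 8 | 2 |
| Decision Self-Efficacy | 11 | 0 |
| Decisional Conflict | 16 | 0 |
| Values survey | 14 | 6 |
| Preparation for Decision Making | 10 | 0 |
| Knowledge Survey | 25 | 0 |
| Choice Predisposition and Decision | 1 | 4 |
| Stage of Decision Making | 10 | 0 |
| **Total** | **95** | **12** |

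95 + 12 = 107. Multiple choice: 95/107 = 89%. Free text: 12/107 = 11%. Realistic Expectations (multiple choice, no count given) and the symptom and function short forms are left out. The involvement scale named under Expected Outcomes is not in this list, so it is not counted either.

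**2. Who judges, and what masking is described.**

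| Source of data | Who judges | Knowledge of arm | Masking described |
|---|---|---|---|
| Fixed-response scales | Participant | Knows it | None |
| Free-text survey items | Reviewer | Masked | Yes |
| Readiness form | Cohort C provider | Told of participation; arm not mentioned | None |
| Visit 3 interview | Interviewer | The topic reveals it | None; impractical |
| Coded transcripts | Coder | Not stated; cues may remain in the text | None |

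Only one row is covered by the stated safeguard.

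**3. Link to the sample-size outcome.** Sample Size Calculations assumes involvement of 30% against 60%, significance level 0.05, 90% power and 55 per group. The two-sided pooled formula, with mean proportion 0.45, is

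n = [1.960 × √(2 × 0.45 × 0.55) + 1.282 × √(0.30 × 0.70 + 0.60 × 0.40)]² / 0.30² = 55.7,

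that is 56 per group, or 112 in total, against the stated 110. The plan's figure is reproduced closely, and masking does not alter it. Expected Outcomes measures involvement with a perceived-involvement scale. It is self-report, so reviewer masking does not protect it.

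**4. Illustration for self-reported involvement only.** Assume no true effect (30% in both arms), 55 per arm, and that knowing the arm raises reported involvement in the aid arm by d points. The size of d is an assumption; the documents give none. The exact two-sided rejection probability is the sum of the binomial probabilities of all outcomes where |z| > 1.96, with z the pooled two-proportion statistic:

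| d (points) | Rejection probability |
|---|---|
| 0 | 5.1% |
| 5 | 9.0% |
| 10 | 20.3% |
| 15 | 37.6% |

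**The case against.** The strongest reply has four parts.

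- **Silence is not disclosure.** A reader might infer that providers and coders know the arm. The documents do not say so: providers learn that the patient takes part, and coders' knowledge is not addressed. This stands, so the point is that no masking is described. Silence still cannot support a claim of avoidance.
- **Reviewer masking has a use.** A reader might conclude that it is worthless. It is not: it protects the scoring of the 12 free-text items and should be kept.
- **The rejection figures do not carry over.** A reader might apply them to readiness ratings or theme counts. The documents plan no between-arm test of either and do not give the response format of the provider form. With up to 50 providers, one may rate several patients, so independent binomials need not hold. The 55 per arm belongs to the involvement comparison, and the figures are confined to it.
- **The design is necessarily open, and the safeguard names only surveys.** Participants cannot be masked to website access, and the sentence does not expressly extend to interviews or provider ratings. Both are true. The open design is not the fault. However, the sentence claims to avoid a whole class of bias, and even for surveys that holds for only a small share of the items.

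**Conclusion.** The point holds as a mismatch between a stated protection and the procedures described. Reviewer masking can guard at most 12 of the 107 counted items per survey set. The Cohort A scales, including the perceived-involvement measure behind the sample size, are completed by participants who know their arm. For Cohort C ratings and interview coding, where observers do judge, no masking is described. Interviewers cannot practically be masked, because the Visit 3 interview asks about the method received.

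The documents do not show that bias will occur, or how large it would be. The rejection probabilities of about 9%, 20% and 38% depend wholly on the assumed tilt, the 30% base rate and a yes/no involvement outcome. The sample size is unaffected. The wording and two procedures should be changed.

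**What to change.** 1. **Coding.** Have transcripts coded under participant ID by coders who are not given the arm. Remove explicit arm labels where this does not delete the content to be coded; comments on website features are part of what the interview seeks and must stay. Attach arm codes only after coding is locked.
2. **Cohort C.** Research staff do not disclose the arm to providers. Add one item to the form recording whether the provider knows it, and report these ratings as unmasked. The second questionnaire is timed to a Cohort A visit 4 that the schedule does not contain. Reconcile this, because controls may use the aid in the cross-over.
3. **Wording.** In Avoidance of bias, limit the claim to masked scoring of free-text survey items and masked coding. State that participant-completed scales and interviews are unmasked, so between-arm differences on them may partly reflect expectation.

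The cost is revised wording, one item on a form expected to take no more than 5 minutes, and extra work on transcripts that are already edited for names. Finding arm labels takes more judgement than replacing names, and some cues will remain. The stated protection becomes less favourable. No added participants or visits are needed.
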